#### 11.3. **Statistical Analysis Methods**

All data will be analyzed using Statistical Analysis System (SAS Version 9.3 or higher for Windows, SAS Institute, Cary, NC). Continuous variables will be summarized using number, mean, standard deviation, median, minimum, and maximum. Categorical variables will be summarized using number and frequencies.

#### 11.3.1. **Safety Analysis**

#### 11.3.1.1. Adverse Events

All safety endpoints will be summarized using descriptive statistics and will be based on the FAS dataset.

All AEs will be coded based on the Medical Dictionary for Regulatory Affairs (MedDRA; Version 17.0 or higher). An AE will be considered a treatment emergent adverse event (TEAE) if the onset is after the first dose of study drug or if the condition was present at baseline but worsened after the first dose.

All AEs for each subject will be listed, including intensity grading, relationship to study drug, action taken and outcome. Subject listings of deaths, SAEs, and AEs leading to treatment discontinuation will be provided. Subject narratives will be provided for deaths, SAEs and other significant AEs. Summary tables will be prepared to examine TEAE severity and relationship to study treatment.

Confidential 57 December 31, 2019 Protocol Amendment 4

AE summaries will be produced separately for each dose cohort and overall, each disease cohort by dose and overall, and by monotherapy combination phases of the study. All summaries will show, by subject group, dose cohort and overall, the number and percentage of subjects experiencing at least 1 TEAE of each preferred term, arranged by system organ class, and the number of occurrences of the event. Separate summaries will be produced by relationship to study medication, by severity, and for those events with an incidence rate of at least 2% in any group or overall.

SAEs will be summarized in a similar manner; overall, by relationship to study medication, and by severity.

In addition to the above, summaries of the number and percentage of subjects discontinuing the study due to AEs and, due to death, will be presented.

#### 11.3.1.2. Laboratory Data

Laboratory data will be listed by subject. Values above and below normal ranges will be indicated, and whether statistically significant. All laboratory values will be graded according to the NCI-CTCAE version 4.03 criteria. Laboratory data will be summarized by actual value and change from baseline using number of non-missing observations, mean standard deviation, median, minimum and maximum. In addition, shift tables and the incidence of Grade 3 or 4 laboratory values will be presented.

#### **11.3.1.3.** Vital Signs

Vital signs will be listed by subject. Values above and below normal ranges will be indicated as will clinical significance. Vital sign data will be summarized by actual value and change from baseline using number of non-missing observations, mean, standard deviation, median, minimum and maximum.

#### 11.3.1.4. Other Safety Data

Data collected for physical examinations, ECGs and related measures will be listed.

#### 11.3.2. Efficacy Analysis

#### 11.3.2.1. Primary Efficacy Endpoint

The primary efficacy endpoint is the proportion of subjects with intracranial OR following E6201 plus dabrafenib treatment. Intracranial response rates will be summarized using number and percentage of subjects with a best response of CR, PR, SD or PD assessed by RECIST v. 1.1 and RANO-BM, along with 2-sided, 95% confidence intervals for the proportions.

#### 11.3.2.2. Secondary Efficacy Endpoints

Non-CNS systemic disease response rates will be determined by RECIST v 1.1. For determination of intracranial disease duration of response, duration of stable disease and time to progression of CNS metastases, and for PFS and overall survival, the Kaplan-Meier product- limit method will be used to estimate the median survival. Subjects who do not have disease progression will be censored at the last follow-up time.

Confidential 58
December 31, 2019 Protocol Amendment 4

Duration of intracranial disease response or stable disease will be calculated from the date of first response or stable disease to the date of progression or death.

Time to progression of CNS metastases will be calculated from the date of first treatment to the date of first evidence of progression of intracranial lesions.

Progression-free survival will be calculated from the date of first treatment to the date of first evidence of progression or death.

Overall survival will be calculated from the date of first treatment to the date of death from any cause; subjects who do not experience death will be censored at the last follow-up time.

SAS Version 9.3 for Windows (SAS Institute, Cary, NC) or higher will be used for all analyses.

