Blood for hematology and serum chemistry determinations will be collected within 28 days of Cycle 1 Day 1 and on Day 1 of each cycle and at the End of Treatment Visit.

ECGs will be taken within 28 days prior to Cycle 1 Day 1, pre-infusion and 5 minutes following the end of the E6201 2-hour infusion, on Day 1 of every cycle thereafter, and at the End-of-Study visit.

CNS and non-CNS systemic disease assessments will be based on magnetic resonance image (MRI) or computed tomography (CT) if unable to perform MRI for intracranial disease. Assessments will be obtained at Week 8 and every 8 weeks thereafter until documented progression of disease (PD). Subjects who demonstrate clinical benefit will be allowed to continue therapy until progression of disease, observation of unacceptable adverse events, intercurrent illness or changes in the subject's condition that prevents further study participation.

Safety will be assessed through the monitoring of adverse events (AEs), clinical laboratory parameters (hematology and serum chemistry), vital sign measurements, ECGs and physical examinations. Adverse events will be classified according to the Medical Dictionary for Regulatory Affairs (MedDRA) and graded according to the National Cancer Institute Common Terminology Criteria for Adverse Events (NCI CTCAE) version 4.03.

Efficacy assessments will be determined on the basis of MRI and/or CT scans with best treatment response at any protocol-specified time point for intracranial disease, duration of response, duration of stable disease, and time to CNS metastasis disease progression based on RECIST v.1.1 and RANO-BM. Response rates also will be determined for non-CNS systemic disease. Progression-free survival (PFS) and overall survival (OS) will be evaluated.

A correlation will be made between *BRAF* mutational status (e.g., type, heterozygosity or homozygosity) in archival tissue with clinical outcome.

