#### 10.4.1.2. Secondary Efficacy Endpoints

To evaluate intracranial disease duration of response, duration of SD and time to progression of CNS metastases, progression-free survival and overall survival, as defined below:

- Duration of Response: length of time from the first evidence of objective response (CR, PR) of intracranial disease lesions to the first objective evidence of progression
- Duration of Stable Disease: length of time from first evidence of stable disease of intracranial disease lesions (CR, PR, SD) to for objective evidence of disease progression or death, whichever is earlier
- Time to Progression of CNS Metastases: length of time from date of first administration of study drug to first objective evidence of disease progression of intracranial lesions
- Progression-Free Survival: length of time from the date of first administration of study drug to the first objective evidence of disease progression or death, whichever is earlier
- Overall Survival: length of time from the date of first administration of study drug to the date of death from any cause.

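### The general censoring sentence contradicts the plan's own definitions of PFS and of the intracranial durations that end at death

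*Combined protocol and SAP*

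**What the plan says.** Section 11.3.2.2 names the intracranial durations and time to CNS progression, and continues: "and for PFS and overall survival, the Kaplan-Meier product- limit method will be used to estimate the median survival". The next sentence is the only general censoring rule: "Subjects who do not have disease progression will be censored at the last follow-up time". The Statistical Methods part of the synopsis carries the same sentence.

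The same section then defines the endpoints one by one:

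- **PFS:** "Progression-free survival will be calculated from the date of first treatment to the date of first evidence of progression or death". Section 10.4.1.2 agrees and runs PFS "to the first objective evidence of disease progression or death, whichever is earlier".
- **Duration of response and of stable disease:** "Duration of intracranial disease response or stable disease will be calculated from the date of first response or stable disease to the date of progression", and the sentence goes on to name death as the alternative end. The synopsis says the same. Section 10.4.1.2 includes death for stable disease but ends duration of response at progression only.
- **Time to CNS progression:** ends at intracranial progression; death is not part of it.
- **OS:** has its own rule, "subjects who do not experience death will be censored at the last follow-up time".

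No other endpoint has its own censoring rule. The term for the last follow-up time is not defined.

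**The concern.** The censoring sentence turns on progression alone, while three of the endpoints it covers also end at death. Followed literally, it changes PFS and duration of stable disease into time-to-progression estimates in which deaths are censored. It does the same to duration of response as 11.3.2.2 defines it. A Kaplan-Meier analysis that censors deaths treats those subjects as if they would have gone on to the same progression risk as the survivors, which is not what PFS is meant to measure.

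The conflicting record can arise in this trial. Imaging is every 8 weeks (5.1), and ECOG 2 and symptomatic CNS metastases are allowed (6.1). Neither the End of Treatment visit (9.5) nor long-term follow-up (9.6, survival only) lists a disease assessment. A subject can therefore have a recorded death and no progression scan. Two analysts could report different PFS from the same data, each with support in the text.

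**Working it through.** The plan states no PFS median, event count or expected share of deaths without progression, so there is no figure to reproduce. The check is textual first; the arithmetic is illustrative.

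**1. One record under both statements.** First dose on Day 1, stable scan in Week 8, death in Week 12, no progression scan.

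| Endpoint | By definition | By the general sentence |
|---|---|---|
| PFS | event, Week 12 | censored |
| Duration of stable disease | ends, Week 12 | censored |
| Time to CNS progression | no event | censored (consistent) |
| OS | event, Week 12 | governed by its own rule |

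A responder who dies without progression has the same conflict for duration of response under 11.3.2.2 and the synopsis, but not under 10.4.1.2.

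**2. Direction if censoring is at the date of death.** The subject leaves the risk set at the same time either way. The only change is that the factor (1 - d/n) at that time becomes 1. The curve can then never lie below the curve with deaths as events.

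**3. Size under constant hazards.** Let M be the true PFS median, so the total hazard is ln 2 / M. Let q be the share of PFS events that are deaths without progression. Censoring those deaths leaves the progression hazard (1 - q) ln 2 / M, so the estimated median tends to M/(1 - q). Both q and M = 4 months are assumptions.

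| q | Multiplier 1/(1 - q) | Median if M = 4 months |
|---|---|---|
| 10% | 1/0.9 = 1.11 | 4.4 |
| 20% | 1/0.8 = 1.25 | 5.0 |
| 30% | 1/0.7 = 1.43 | 5.7 |

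**4. Check at the planned size.** Simulation with 18 subjects, exponential times, M = 4 months, administrative censoring uniform on 6 to 30 months, 5,000 runs per setting. The typical Kaplan-Meier median with deaths as events was 3.7 months throughout; it lies below 4 because of the small sample. With deaths censored it was 4.3, 4.9 and 5.7 months for q = 10%, 20% and 30%.

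**5. An example that can be done by hand.** Eighteen subjects leave at times 1 to 18, and those at 3, 6, 9, 12, 15 and 18 are deaths without progression. With deaths as events, S(9) = 9/18 = 0.5, so the median is 9. With deaths censored, S(11) = (16/18)(13/15)(10/12)(7/9) = 0.499, so the median is 11.

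**6. Direction if last follow-up falls before death.** Subject A is last followed at month 2 and dies at month 10; B progresses at month 5. With A's death as an event, both are at risk at month 5 and S(6) = 1/2 = 0.5. With A censored at month 2, only B is at risk and S(6) = 0. The curve falls because the risk set shrinks early.

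**The case against.** The strongest reply is that the definitions settle the matter. Death is a PFS event in the synopsis, in 10.4.1.2 and in 11.3.2.2, where the definition follows the general sentence. A specific definition usually governs a general line, and the general line cannot be meant literally for its whole list, since that list includes OS. The natural reading would be that subjects without the event are censored. This is plausible, and it means a reader should not infer that the analysis would in fact censor deaths. But no section says that the definition prevails, and writing a death-based rule for OS alone leaves the general sentence as the only rule for the rest.

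Three stronger readings are tempting and are not supported:

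- **That the bias is always towards longer PFS.** Step 6 of the working shows otherwise when last follow-up falls before death, and the plan does not define that date.
- **That the monotherapy phase already shows deaths without progression.** Section 3.4.1 reports that one of four subjects left for worsening mentation. It does not say that this subject died. Under RANO-BM (Appendix F) worse clinical status is itself a progression criterion.
- **That such deaths will be common.** Section 6.1 requires a life expectancy of at least 3 months, 6.2 excludes subjects in urgent need of treatment, and 10.4.2 allows extra assessments. The documents give no rate.

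It is also fair that the effect could be small. At q = 10%, about two of 18 subjects (0.1 × 18 = 1.8) would be involved, and the median would shift by about 0.4 months, less than one 8-week scan interval.

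**Conclusion.** The contradiction stands, in both 11.3.2.2 and the synopsis. It affects PFS and duration of stable disease, and duration of response as those two places define it. It does not affect OS, and the general sentence does not conflict with the definition of time to CNS progression.

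If deaths are censored on the date of death, PFS is biased upward, with the median multiplied by 1.11 to 1.43 for q between 10% and 30%. That range rests on constant hazards and an assumed q, and the values in months on an assumed median of 4 months. If last follow-up falls before death, local distortion in the other direction is possible. The contradiction itself needs none of these assumptions.

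A reader might infer that the trial's conclusion is at risk. It is not: the rule for moving forward in 11.1 uses intracranial response only, and the affected endpoints are secondary and descriptive, with no test or threshold.

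**What to change.** Replace the general sentence in 11.3.2.2 and in the synopsis with a rule for each endpoint:

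- **PFS and duration of stable disease:** death without prior progression is an event on the date of death. Subjects who have neither progressed nor died are censored at a stated date, for example the last evaluable disease assessment.
- **Time to CNS progression:** keep censoring of subjects without intracranial progression, and state the date.
- **Duration of response:** first reconcile 10.4.1.2 (progression only) with 11.3.2.2 and the synopsis (progression or death), then apply the matching rule.
- **OS:** no change.

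The cost is a few sentences in two places. Data collection, sample size and treatment do not change. The one downside is that reported PFS may be shorter than under the literal rule.

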#### 11.3.3. Pharmacodynamic Endpoint Analysis

A correlation will be made between *BRAF* mutational status (e.g., type, heterozygosity or homozygosity) in archival tissue with clinical outcome.

Confidential 59
December 31, 2019 Protocol Amendment 4

#### 12. STUDY MANAGEMENT

#### 12.1. Data Management

The investigator is responsible for completing and maintaining adequate and accurate source documentation. Source documentation constitutes original records, which may include progress notes, medication administration records, laboratory reports, ECG tracings, discharge summaries, CRF worksheets, etc. Data for this study will be submitted electronically. Access to the database will be provided following a brief on-line training session. Each user will receive a unique username and password, which should not be shared. The investigator must sign the investigator's statement for each subject indicating that the data reported are accurate.

#### **12.2.** Monitoring

The sponsor, Spirita Oncology, is responsible for ensuring the proper conduct of the study with regard to ethics, protocol adherence, site procedures, integrity of the data, and applicable laws and/or regulations. At regular intervals during the study and following completion of the study, the sponsor's study monitors will contact the study site via visits to the site, telephone calls, and letters in order to review study progress, CRF completion, and address any concerns or questions regarding the study conduct. During monitoring visits, the following aspects of study conduct will be carefully reviewed: informed consent of subjects, subject recruitment, subject compliance with the study procedures, source data verification, drug accountability, use of concomitant therapy by subjects, AE and SAE documentation and reporting, and quality of data. Records pertaining to these aspects are expected to be kept current.

#### 12.3. Audits and Inspections

Authorized representatives of Spirita Oncology, a regulatory authority, an Independent Ethics Committee or an Institutional Review Board may visit the site to perform audits or inspections, including source data verification. The purpose of a Spirita Oncology audit or inspection is to systematically and independently examine all study-related activities and documents to determine whether these activities were conducted, and data were recorded, analyzed, and accurately reported according to the protocol, Good Clinical Practice guidelines of the International Conference on Harmonization, and any applicable regulatory requirements. The investigator should contact Spirita Oncology immediately if contacted by a regulatory agency about an inspection.

#### 12.4. Amendments

Any amendments to the protocol will be written and approved by Sponsor, Spirita Oncology. All amendments must be submitted to the IRB for approval prior to implementing the changes. In some instances, an amendment requires changes to the informed consent form, which also must be submitted for IRB approval prior to administration to subjects. If any changes to the CRF are required, Spirita Oncology will issue supplemental or revised CRF pages on behalf of the sponsor.

Confidential 60
December 31, 2019 Protocol Amendment 4

## 12.5. Institutional Review Board (IRB)

The Principal Investigator must obtain IRB approval for the investigation. Initial IRB approval, and all materials approved by the IRB for this study including the subject consent form and recruitment materials must be maintained by the Investigator and made available for inspection.

## 13. QUALITY CONTROL AND QUALITY ASSURANCE

To ensure compliance with Good Clinical Practices and all applicable regulatory requirements, Spirita Oncology, LLC may conduct a quality assurance audit. See Section 12.3 for more details regarding the audit process.

#### 14. ETHICS

#### 14.1. Ethics Review

The final study protocol, including the final version of the Informed Consent Form, must be approved or given a favorable opinion in writing by an IRB or IEC as appropriate. The investigator must submit written approval to Spirita Oncology, LLC before he or she can enroll any subject into the study.

The Principal Investigator is responsible for informing the IRB or IEC of any amendment to the protocol in accordance with local requirements. In addition, the IRB or IEC must approve all advertising used to recruit subjects for the study. The protocol must be re-approved by the IRB or IEC upon receipt of amendments and annually, as local regulations require.

The Principal Investigator is also responsible for providing the IRB with reports of any reportable serious adverse drug reactions from any other study conducted with the investigational product. Spirita Oncology will provide this information to the Principal Investigator.

Progress reports and notifications of serious adverse drug reactions will be provided to the IRB or IEC according to local regulations and guidelines.

#### 14.2. Ethical Conduct of the Study

The study will be performed in accordance with ethical principles that have their origin in the Declaration of Helsinki and are consistent with ICH/Good Clinical Practice, applicable regulatory requirements and corporate policy on Ethical Standards (APPENDIX G).

#### 14.3. Written Informed Consent

The Principal Investigator(s) at each center will ensure that the subject is given full and adequate oral and written information about the nature, purpose, possible risk and benefit of the study. Subjects must also be notified that they are free to discontinue from the study at any time. The subject should be given the opportunity to ask questions and allowed time to consider the information provided.

The subject's signed and dated informed consent must be obtained before conducting any study procedures.

The Principal Investigator(s) must maintain the original, signed Informed Consent Form. A copy of the signed Informed Consent Form must be given to the subject.

Confidential 63
December 31, 2019 Protocol Amendment 4

#### 15. DATA HANDLING AND RECORDKEEPING

#### 15.1. Health Insurance Portability Accountability Act of 1996

The investigator agrees to comply with all applicable federal, state, and local laws and regulations relating to the privacy of subject health information, including, but not limited to, the Standards for Individually Identifiable Health Information, 45 CFR. Parts 160 and 164 (the Health Insurance Portability Accountability Act of 1996 [HIPAA] Privacy Regulation). The investigator shall ensure that study subjects authorize the use and disclosure of protected health information in accordance with HIPAA Privacy Regulation and in a form satisfactory to the sponsor.

#### 15.2. Financial Disclosure

The investigator shall provide to the sponsor sufficient accurate financial information to allow Spirita Oncology to submit complete and accurate financial certification or disclosure statements to the FDA. The investigator shall promptly update this information yearly and for one year following completion of the study.

#### 15.3. Inspection of Records

Spirita Oncology will be allowed to conduct site visits to the investigation facilities for the purpose of monitoring any aspect of the study. The Investigator agrees to allow the monitor to inspect the drug storage area, study drug stocks, drug accountability records, subject charts and study source documents, and other records relative to study conduct.

## **15.4.** Access to Original Records

It is an expectation of regulatory authorities that monitors, auditors, and representatives of national and international government regulatory agency bodies have access to original source documentation to ensure data integrity. "Original" in this context is defined as the first documentation of an observation and does not differentiate between hard copy and electronic records.

